Study Enrollment and Consent: Postpartum nurses and providers will be invited to participate in individual in-depth interviews about their perceptions of IPP-HPV. All participants will receive informed consent (see attached) and a \$25 VISA card will be provided as an incentive to providers that participate.

Sampling: We will aim to have a purposive sample with representation by provider type and clinical setting/location.

1.3.3 Data collection: The in-depth individual interviews will be conducted using a semi-structured guide (see attached) based on Consolidated Framework for Implementation Research (CFIR) constructs. We will focus on CFIR constructs belonging to domains which we consider to be most relevant to IPP-HPV implementation from the providers' perspective: *Intervention Characteristics* (e.g., perceived advantages and adaptability of the intervention), the *Inner Setting* (e.g., structural and cultural contexts within the clinical setting), and *Characteristics of Individuals* (e.g., knowledge and beliefs about the intervention).

1.3.4 Data analysis: Recorded interviews will be transcribed and transcripts analyzed using standard analytic methods for qualitative data as described above (see Aim 2). Provider receptivity of IPP-HPV and perceptions of patient acceptance will be categorized by themes. Perceived barriers to and facilitators of IPP-HPV will be described and will further inform future implementation of IPP-HPV. Demographic data about postpartum providers will be tabulated. Quantitative data from the pre- and post-intervention provider surveys will be tabulated and differences compared using bivariate analysis.

1.4 Specific Aim 3

To assess the uptake and effectiveness of a Pilot Quality Improvement Program to increase HPV vaccine uptake (IPP-HPV) for Yale New Haven Hospital (YNHH) Women's Center and Center for Women's Health and Midwifery (CWHM) postpartum patients ≤ 26 years of age who deliver at YNHH

York Street Campus (YSC) or Saint Raphael Campus (SRC).

1.41 **Study participants:** Women’s Center and CWHM postpartum patients ≤ 26 years of age who have received less than 3 doses of the HPV vaccine prior to delivery and who deliver at YNHH YSC or SRC during the two years of the IPP-HPV Program as well as Women’s Center and CWHM postpartum patients ≤ 26 years of age who delivered at YNHH YSC/SRC in the year preceding implementation of the IPP-HPV Program.

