1.42 **Study design:** Medical record review from above patients to review each patient’s immunization record and related clinical visits in the 30 months after delivery.

1.43 **Data Collection:**
The following data will be recorded from the chart (i.e., MRN, name, diagnosis):

- MRN
- Patient ID
- Name
- DOB
- Race
- Ethnicity
- Marital status
- Religion
- Primary Language
- Education
- Zip Code
- Insurance Type (Payor Name, Benefit Class, Benefit Plan Name)
- Smoking Status
- Gravidity
- Parity
- HIV status
- Allergies
- Number of clinic visits to WC or CWHM during 30 months following delivery
- Provider Name
- Provider Type
- Dates of visits
- Visit type
- HPV vaccination status at each encounter
- Dates that each HPV vaccine was ordered.
- Vaccine Type (i.e., quadrivalent vs 9-valent, etc)
- Vaccine number/rank (#1, 2, or 3 in the series)
- Name of provider who ordered each vaccine.
- Date that each HPV vaccine was administered.
- Were any other vaccines administered during the 30 months following delivery?
- If yes, which ones and on what dates?
- Were any other injectable medications administered during the study period?
- If yes, which ones and on what dates?

- Was HPV vaccine due?
- Was HPV vaccine offered/discussed?
- Was HPV vaccine ordered?
- Was HPV vaccine administered?
- Was HPV vaccine declined?
- If declined, what was the reason for decline?
- Were other postpartum vaccines (Tdap, flu, MMR) due?
Administered/declined?

Measures that will be used from the IPP-HPV program to assess its implementation will include number of women eligible for HPV vaccine, proportion accepting a dose of HPV vaccine while inpatient, proportion who agree to be vaccinated but do not receive the vaccine dose, and identification of possible barriers to implementation of IPP-HPV (e.g., nurses are too busy, patients leave prior to vaccine administration, vaccine order not placed). In addition, we will abstract data from questionnaires voluntarily submitted by postpartum nurses to the IPP-HPV Program on their experience with each patient related to HPV immunization.

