We will obtain data on receipt of subsequent doses of vaccine and on completion of the 3-dose series of the vaccine by medical chart review. Dates of receipt of HPV vaccine, date of postpartum visit, and data on whether a dose of HPV vaccine was due at the postpartum visit and, if so, whether dose was received will be recorded. Data on the need for and receipt of postpartum Tdap, influenza and rubella vaccines will also be obtained from medical chart review for comparison. Demographic and clinical information will also be obtained. Historical data on the HPV vaccination history of all WC patients \leq 26 years old who delivered in the 12 months prior to implementation of IPP-HPV will also be collected for comparison of their rates of vaccine series completion (from outpatient administration) within 30 months of delivery.

144

Data analysis: We will tabulate measures as follows:

- IPP-HPV Acceptance: Proportion of eligible patients agreeing to receive a dose of vaccine
- HPV Vaccine Administration: Proportion of eligible patients that agree to be vaccinated who actually receive dose of vaccine as an inpatient.
- Barriers to vaccination: descriptive data on potential barriers to receiving the vaccine postpartum
- Other vaccines: Proportion of eligible patients due for Tdap, influenza or MMR vaccines and proportion that receive each

To assess the effectiveness of the pilot IPP-HPV immunization program we will tabulate the proportion of postpartum women eligible for the vaccine who receive a dose of HPV vaccine, the proportion of participants that need 1, 2, or 3 vaccine doses that receive the respective number of doses within up to 30 months of postpartum discharge, the proportion of all participants that complete the vaccine series within 12 months and within 30 months, and the proportion of study participants that complete the vaccine series within 12 months and within 30 months that received IPP-HPV.

Multivariable logistic regression will be used to determine predictors of inpatient postpartum HPV vaccine uptake and of vaccine completion (e.g., age, parity, race, ethnicity). The difference in proportion of women who complete the 3-dose series within 12 months and within 30 months of postpartum discharge in the study cohort and in the group of Women's Center patients who delivered in the 12 months prior to implementation of IPP-HPV will be compared using chi square analysis.

1.5 Specific Aim 4

151 Study participants:

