To evaluate receptivity and concerns of healthcare providers with inpatient postpartum HPV immunization as part of IPP-HPV and to identify facilitators of and barriers to its implementation.

Study participants: YNHH inpatient and Women's Center outpatient postpartum nurses, and obstetric providers affiliated with the Women's Center or Center for Women's Health and Midwifery, including nursing and medical directors, will be eligible to participate. We will aim to have a purposive sample of about 15 participants with representation by provider type and clinical setting/location.

Specific Aim 3

To assess the uptake and effectiveness of a Pilot Quality Improvement Program to increase HPV vaccine uptake (IPP-HPV) for Yale New Haven Hospital (YNHH) Women's Center and Center for Women's Health and Midwifery (CWHM) postpartum patients \leq 26 years of age who deliver at YNHH

York Street Campus (YSC) or Saint Raphael Campus (SRC).

Study participants: Women's Center and CWHM postpartum patients \leq 26 years of age who have received less than 3 doses of the HPV vaccine prior to delivery and who deliver at YNHH YSC or SRC during the first year of the IPP-HPV Program as well as Women's Center and CWHM postpartum patients \leq 26 years of age who delivered at YNHH YSC/SRC in the year preceding implementation of the IPP-HPV Program.

Specific Aim 4

To identify the processes utilized to integrate delivery of vaccines that are currently administered routinely during inpatient postpartum care

Study participants: Observational workflow analysis-YNHH (YSC or SRC) inpatient postpartum nurses or inpatient obstetric providers; In-depth individual interviews--YNHH

(YSC or SRC) inpatient postpartum nurses, inpatient obstetric providers, hospital pharmacy representatives or EMR analysts

Specific Aim 5

To iteratively develop an EMR-based tool that promotes integration of IPP-HPV immunization into routine inpatient postpartum care and conduct a survey prior to implementation of IPP-HPV to assesses the knowledge, attitudes and beliefs of HPV vaccine and IPP-HPV by OB healthcare workers across YNHHS.

Study participants: YNHHS inpatient postpartum nurses, inpatient obstetric providers, hospital pharmacy representatives or EMR analysts

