6. **Subject classification:** Check off all classifications of subjects that will be specifically recruited for enrollment in the research project. Will subjects who may require additional safeguards or other considerations be enrolled in the study? If so, identify the population of subjects requiring special safeguards and provide a justification for their involvement.

 Children	 Healthy	 Fetal material, placenta, or dead fetus
 Non-English Speaking	 Prisoners	 Economically disadvantaged persons
 Decisionally Impaired	 Employees	 Pregnant women and/or fetuses
 Yale Students	 Females of childbearing potential	

NOTE: Is this research proposal designed to enroll children who are wards of the state as potential subjects? **Yes** **No**

7. **Inclusion/Exclusion Criteria:** What are the criteria used to determine subject inclusion or exclusion?

Specific Aim 1: Patient Qualitative Interviews

Inclusion:

- Women participating in the IPP-HPV Quality Improvement Program:
 - Postpartum YNHH Women's Center and CWHM patients
 - ≤ 26 years at time of delivery who deliver at YNHH YSC or SRC
 - Have not already received 3 doses of the HPV vaccine at time of delivery
- Fluent in English or Spanish
- Able and willing to provide consent

Specific Aim 2: Provider Qualitative Interviews

Inclusion:

- YNHH inpatient postpartum nurses or Women's Center outpatient postpartum nurses or inpatient or outpatient obstetric providers affiliated with the Women's Center or Center for Women's Health and Midwifery
- Able and willing to provide consent

Specific Aim 3: Medical Records Review

Inclusion:

- Yale New Haven Hospital (YNHH) Women's Center and Center for Women's Health

and Midwifery (CWHM) postpartum patients

- ≤ 26 years of age
- Delivered at YNHH York Street Campus (YSC) or Saint Raphael Campus (SRC) in the first year of the IPP-HPV program or in the one year preceding implementation of the program

Specific Aim 4:

Observational Workflow Analysis

Inclusion:

- YNHH (YSC or SRC) inpatient postpartum nurses or inpatient obstetric providers

Provider/Staff Qualitative

Interviews Inclusion:

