- i. Describe why it would be impracticable to obtain the subject's authorization for use/disclosure of this data:

It will not be possible to retrospectively reach and obtain authorization for medical chart review of all postpartum women from the Women's Center and CWHM who delivered in the year prior to or in the first year of implementation of the quality improvement program.

- ii. If requesting a waiver of **signed** authorization, describe why it would be impracticable to obtain the subject's signed authorization for use/disclosure of this data:

The investigator assures that the protected health information for which a Waiver of Authorization has been requested will not be reused or disclosed to any person or entity other than those listed in this application, except as required by law, for authorized oversight of this research study, or as specifically approved for use in another study by an IRB.

Researchers are reminded that unauthorized disclosures of PHI to individuals outside of the Yale HIPAA-Covered entity must be accounted for in the "accounting for disclosures log", by subject name, purpose, date, recipients, and a description of information provided. Logs are to be forwarded to the Deputy HIPAA Privacy Officer.

6. Process of Consent/Accent: Describe the setting and conditions under which consent/assent will be obtained, including parental permission or surrogate permission and the steps taken to ensure subjects' independent decision-making.

Postpartum inpatient or outpatient nurses and clinicians will refer postpartum patients (and a parent/guardian if patient is <18 years of age) in the Inpatient Postpartum HPV Immunization Program who are interested in the study to project staff while Obstetrics Providers, Pharmacy staff and EMR analysts who are interested in the study will directly contact project staff; both will be screened for

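### The Aim 3 historical comparison group is Women's Center plus CWHM in the cohort definitions but Women's Center alone in the chi-square comparison

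*Combined protocol and SAP*

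**What the plan says.** Two descriptions of the pre-program group stand side by side in the current text.

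**Both clinics:**
- Research Plan 1.41 names the Women's Center together with "CWHM postpartum patients ≤ 26 years of age who delivered at YNHH YSC/SRC in the year preceding implementation of the IPP-HPV Program".
- 1.42 ties the chart review to that cohort: "Medical record review from above patients".
- Section I item 5 (Subject Population, Aim 3) repeats the two-clinic definition: "first year of the IPP-HPV Program as well as Women's Center and CWHM postpartum patients".
- Section I item 7 (Inclusion criteria, Aim 3) has one clinic criterion, "Yale New Haven Hospital (YNHH) Women's Center and Center for Women's Health" and Midwifery, and applies it to deliveries "in the first year of the IPP-HPV program or in the one year preceding implementation of the program".
- The HIPAA and consent waiver requests (Section III items 5 and 9) cover "all postpartum women from the Women's Center and CWHM who delivered in the year prior to or in the first year of implementation".

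**Women's Center only:**
- 1.43 describes the comparison data as "Historical data on the HPV vaccination history of all WC patients" in the age range.
- The chi-square sentence in 1.44 compares completion "in the study cohort and in the group of Women's Center patients who delivered in the 12 months prior to implementation of IPP-HPV". Section I item 12 uses the same words.

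**The concern.** The narrow wording sits in the sentences that an abstractor and an analyst would follow, and they govern the only between-period tests in Aim 3: 12 and 30 months in 1.44, 12 months in item 12. The planned logistic regression looks for predictors of uptake and completion and is not specified as a comparison of periods.

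If the study cohort means both clinics, as 1.41 and item 5 define it, and the historical group is Women's Center only, clinic mix differs between the two sides. A CWHM advantage in completion would then look like program benefit, and a CWHM disadvantage would hide benefit or look like harm. Whichever reading was meant, two analysts working from different sections would build different comparison groups.

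**Working it through.** **The plan's own figure.** Section III item 1 gives 700 charts for Aim 3, with no error rate, power, completion rates, or split by period or clinic. There is nothing to reproduce.

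**Bias under the literal reading.** Let *s* be the CWHM share of the program cohort and *g* the CWHM completion rate minus the Women's Center rate. With no program effect:

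- historical rate = base
- program rate = base + *s* × *g*
- spurious difference = *s* × *g*

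**Assumed inputs (illustration only).** Base 15%; 350 program charts (half of 700); historical charts 350 × (1 − *s*), which leaves 315, 262 or 210 at shares of 10%, 25% or 40%; two-sided 5% chi-square test without continuity correction.

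**Formula.** With pooled rate p̄, SE0 = √[p̄(1−p̄)(1/n1 + 1/n2)] and SE1 = √[p1(1−p1)/n1 + p2(1−p2)/n2]. The rejection rate is Φ((d − 1.96·SE0)/SE1) + Φ((−d − 1.96·SE0)/SE1).

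**One case in full** (*s* = 40%, *g* = +5 points):
- Program rate 0.15 + 0.40 × 0.05 = 0.17 (n = 350); historical rate 0.15 (n = 210); d = 0.02.
- p̄ = (59.5 + 31.5)/560 = 0.1625; SE0 = 0.0322; SE1 = 0.0318.
- Rejection = 0.087 (apparent benefit) + 0.005 (apparent harm) = 0.092.

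**No program effect, rejection rate of the nominal 5% test:**

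| Clinic gap *g* | share 10% | share 25% | share 40% |
|---|---|---|---|
| 0 | 5.0% | 5.0% | 5.0% |
| +5 points | 5.4% | 6.9% | 9.2% |
| −5 points | 5.4% | 7.3% | 10.6% |
| +10 points | 6.4% | 12.9% | 22.0% |
| −10 points | 6.6% | 14.8% | 28.9% |

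At *g* = +5 points, false claims of benefit are 3.7% to 8.7%, against 2.5% nominal. At *g* = −5 points, nearly all the excess is apparent harm.

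**Sensitivity (5-point gap).**
- Base 13%, the completion figure in Section I item 2 for women aged 18-26: 5.4% to 11.4%.
- A 467/233 split of the 700, which fits the two program years in 1.41 (items 5 and 7 say one), with the historical side cut to 210 or 140 charts: 5.2% to 10.2%.

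**Power with a true 10-point rise in both clinics:**

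| Comparison | share 10% | share 40% |
|---|---|---|
| Two clinics against Women's Center, *g* = −5 points | 86.8% | 63.6% |
| Two clinics against Women's Center, *g* = 0 | 89.7% | 81.3% |
| Both clinics on both sides (350/350), *g* = −5 points | 91.8% | 93.3% |

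The second row shows that part of the loss comes from having fewer historical charts rather than from bias.

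**The case against.** The strongest reply is that this is shorthand. The inclusion criteria apply one clinic rule to both periods, 1.42 points back to the two-clinic cohort, and the waivers cover CWHM charts from the prior year. The Overview (1.1) describes the whole program as being for Women's Center patients, and the Aim 1 recruitment text mentions only Women's Center appointments although Aim 1 admits CWHM patients. Leaving out CWHM may be a drafting habit.

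That is plausible, and the bias is conditional for this reason. It does not settle the matter. The Aim 3 participant definitions name both clinics, and the chart-item list in 1.43 names them separately. The sentences that specify the comparison come after 1.42 and still name one clinic. A reader cannot tell shorthand from a deliberate restriction.

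Three points about the illustration stand:
- Cutting the historical charts without replacing them leaves 560 at a 40% share, below the target of 700. Holding 700 in the same ratio (438/262), power with CWHM 5 points lower is about 74% rather than 64%, and about 89% with no gap. The false-positive rates rise slightly, to roughly 10% and 12%.
- The 13% background figure is general series completion, not completion within 12 or 30 months of delivery.
- At a 10% share with a 5-point gap, the excess error is negligible.

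**Conclusion.** The concern holds. The plan defines the historical comparator in two incompatible ways, and the narrower one is in the test itself. That much needs no assumptions.

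The bias depends on both the literal reading and a real clinic difference in completion. It equals CWHM share × clinic gap, for example 0.5 points at a 10% share and 5-point gap, or 4 points at a 40% share and 10-point gap. Neither its size nor its direction can be derived from the documents. It vanishes if both sides use the same clinics with a stable mix, or if the clinics complete alike. The error rates above show how the mechanism scales and are not estimates for this study. The point should be fixed because it concerns the rule for the only between-period effectiveness comparison and costs almost nothing to correct.

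**What to change.** In 1.43, 1.44 and Section I item 12, define the historical group as Women's Center and CWHM patients delivering in the 12 months before implementation, to match 1.41 and Section I items 5 and 7. This is a wording change in three places; the CWHM prior-year charts are already within the cohort definition and the waiver requests.

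If those charts cannot be used, say so and restrict the program side of the test to Women's Center patients as well. Under the 350/350 assumptions with no clinic gap, that lowers power for a 10-point rise from 91.3% to 88.2% (10% share) or 72.8% (40% share).

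Stratifying by clinic (Cochran-Mantel-Haenszel, or a clinic term in a model) is optional. With the same clinics in both periods and a stable mix, it is not needed to remove this bias. The fallback and the stratification both need each patient's clinic. The list in 1.43 has only a count of visits to either clinic, so the sponsor should confirm that clinic is recoverable from the selection data or add one field.

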old women found effectiveness against precancerous lesions of moderate grade or worse (CIN2+) to be 30.4%.¹ The study also demonstrated a 24.7% reduction in the number of cervical excision procedures for the treatment of precancerous cervical lesions in this cohort.¹ However, studies have shown low rates of initiation (60%) and of completion (40%) of the HPV vaccine series among adolescent females in the United States.⁴ Rates of initiation (30%) and of completion (13%) are even lower for young adult women aged 18-26 years.^{5,6} Among young adult women eligible for HPV vaccine, pregnancy is one factor significantly associated with not completing the vaccine series since the vaccine is not recommended during pregnancy.⁷

Rationale & Significance

Administration of the HPV vaccine during the inpatient postpartum hospital stay has the potential to be an innovative intervention to improve HPV immunization rates. Following onset of pregnancy, the postpartum period becomes the next available opportunity to immunize with the HPV vaccine, which is safe in breastfeeding women. The benefits of such an intervention include a focus on women engaged with the health care system who are often highly motivated to invest in their personal health.

Currently, the HPV vaccine is not routinely available to postpartum women during their inpatient admission. However, by utilizing the immediate postpartum period when women are already in the hospital, we take advantage of access to patients and reduce the number of additional visits needed to complete the vaccine. Immunization of postpartum women on the inpatient floor is already standard practice for women who need Tdap, influenza or MMR vaccines and these programs are associated with increased rates of immunization.^{8,9}

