To assess the effectiveness of the pilot IPP-HPV immunization program we will tabulate the proportion of postpartum women eligible for the vaccine who receive a dose of HPV vaccine, the proportion of participants that need 1, 2, or 3 vaccine doses that receive the respective number of doses within 12 months of postpartum discharge, the proportion of all participants that complete the vaccine series within 12 months, and the proportion of study participants that complete the vaccine series within 12 months that received IPP-HPV.

Multivariable logistic regression will be used to determine predictors of inpatient postpartum HPV vaccine uptake and of vaccine completion (e.g., age, parity, race, ethnicity). The difference in proportion of women who complete the 3-dose series within 12 months of postpartum discharge in the study cohort and in the group of Women's Center patients who delivered in the 12 months prior to implementation of IPP-HPV will be compared using chi square analysis.

Specific Aim 4:

All workflow analysis and individual interviews and will be recorded and subsequently transcribed. We will analyze transcripts and determine common themes and priority domains. Standard analytic methods for qualitative data will be employed.¹⁵ A codebook will be developed based on deductive (theory-driven) constructs from the interview guide and applied to a subset of transcripts. Concordance will be measured and discrepant codes resolved by adjudication using software for qualitative research. We will identify and discuss initial themes and identify inductive

(data-driven) codes. The identification of inductive codes will continue with subsequent coding in an iterative manner. The coded data will be used to iteratively develop process maps for each vaccine and to identify gaps in the process to guide subsequent observations.⁵⁵ The maps will also indicate process variations and identify steps in which EMR tools are utilized.

Specific Aim 5:

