All individual interviews will be recorded and subsequently transcribed. We will analyze transcripts and determine common themes and priority domains. Standard analytic methods for qualitative data will be employed.¹⁵ A codebook will be developed based on deductive (theory-driven) constructs from the interview guide and applied to a subset of transcripts. Concordance will be measured and discrepant codes resolved by adjudication using software for qualitative research. We will identify and discuss initial themes and identify inductive (data-driven) codes. The identification of inductive codes will continue with subsequent coding in an iterative manner. The coded data will be used to develop process maps for each vaccine and understand the needs and preferences of each provider group, as it relates to an EMR-based tool for IPP-HPV immunization.^{51,52} All individual surveys will be recorded and kept anonymous. Participants will be provided a QR code to complete the survey using the Yale Qualtrics platform. We will analyze the knowledge, attitudes, and beliefs of participants in aggregate and by delivery network using descriptive statistics, bivariate and multivariate analyses.

SECTION II: RESEARCH INVOLVING DRUGS, BIOLOGICS, RADIOTRACERS, PLACEBOS AND DEVICES

If this section (or one of its parts, A or B) is not applicable, state N/A and delete the rest of the section.

N/A

SECTION III: RECRUITMENT/CONSENT AND ASSENT PROCEDURES

1. Targeted Enrollment: Give the number of subjects:

a. Targeted for enrollment at Yale for this protocol:

Specific Aim 1: 16-20 patient interviews

Specific Aim 2: 15 provider interviews

Specific Aim 3: 700 medical charts reviewed

Specific Aim 4: 15-20 unique observations and 15-20 interviews with OB providers and nurses and 8-10 interviews with hospital pharmacy and YNHH EMR representatives

Specific aim 5: 15-20 interviews with OB providers and nurses and 8-10 interviews with hospital pharmacy and YNHH EMR representatives. 50 completed surveys from OB related healthcare workers from each of #4 YNHHS sites.

b. If this is a multi-site study, give the total number of subjects targeted across all sites:

N/A

2. Indicate recruitment methods below. Attach copies of any recruitment materials that will be used.

- Flyers
- Posters
- Letter
- Medical Record Review*
- Departmental/Center Newsletters

- Internet/Web Postings
- Mass E-mail Solicitation
- Departmental/Center Website
- Departmental/Center Research Boards

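### Aim 3's effectiveness contrast is an unadjusted before/after chi-square, so any other change between the two periods would be read as a program effect

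*Combined protocol and SAP*

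**What the plan says.** Section I.3, 1.44 opens the Aim 3 outcomes with "To assess the effectiveness of the pilot IPP-HPV immunization program we will tabulate" and lists several proportions vaccinated and completing. The one test against a group without the program follows. Its outcome is "The difference in proportion of women who complete the 3-dose series within 12 months and within 30 months of postpartum discharge". On the comparator, drawn from the Women's Center, the text reads: "who delivered in the 12 months prior to implementation of IPP-HPV will be compared using chi square analysis". Section I.12 repeats the test with a 12-month horizon only ("The difference in proportion of women who complete the 3-dose series within 12 months of postpartum discharge in the study cohort").

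Neither section plans a calendar-time term, an adjustment of this contrast, a control outcome or a caution about secular change. Both plan a multivariable logistic regression for predictors of uptake and completion, with age, parity, race and ethnicity as examples. Period is not named, and the model is not tied to the before/after comparison.

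Other relevant text:

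- **Dose criterion.** 1.41 and Section I.5 limit the program cohort to women with fewer than 3 doses before delivery. The same sentence puts no such limit on the prior-year group. Section I.7 states no dose limit for either period.
- **Program period.** 1.41 counts two program years; Sections I.5 and I.7 count the first year only.
- **Coverage.** Section I.2 reports 60% initiation and 40% completion in adolescents, then "Rates of initiation (30%) and of completion (13%) are even lower for young adult women aged 18-26 years".
- **Other vaccines.** 1.43 says: "Data on the need for and receipt of postpartum Tdap, influenza and rubella vaccines will also be obtained from medical chart review for comparison". What is to be compared is not defined.
- **Size.** Section III.1 gives "Specific Aim 3: 700 medical charts reviewed", with no split by period and no derivation.

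**The concern.** A chi-square on two pooled periods estimates the difference between the periods. It equals the program's effect only if nothing else that bears on completion changed. Several things could have changed: the mix of patients, the number of doses they already had, how outpatient clinics offered the vaccine, and how doses were recorded. One case-mix question is already in the text. 1.41 draws both groups from the Women's Center and CWHM, whereas 1.43 and 1.44 name only Women's Center patients as the comparator.

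The Background adds a reason to expect some drift. Having completed the series cannot be undone, so coverage within a birth cohort cannot fall with age. Higher coverage at 13-17 than at 18-26 therefore suggests that later cohorts are better covered.

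The stake is the conclusion itself. Section V presents documenting effectiveness as a benefit that would help the program expand, so a causal reading of this contrast is the natural one.

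**Working it through.** **1. The plan's own figure.** The 700 charts cannot be reproduced, because no alpha, power, baseline or effect size is given. Assume two-sided 5%, 80% power, 13% baseline completion (borrowed from Section I.2) and equal yearly volume. Then 700 charts detect 7.9 points at 350/350 (one program year) or 8.6 points at 233/467 (two program years).

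**2. Upper bound on birth-cohort drift.** Take mid-ages 15 (ages 13-17, from the title of the cited adolescent source) and 22 (ages 18-26). The gradient in completion is (40 - 13)/(22 - 15) = 27/7 = 3.9 points per birth year. Over age gaps of 9 to 5 years it ranges from 27/9 = 3.0 to 27/5 = 5.4. Period midpoints lie 1 year apart (one program year) or 1.5 years apart (two), so the shifts are 3.86 and 5.79 points.

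**3. False rejection with no program effect.** With shift d, pooled standard error s0 and unpooled standard error s1:

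P(reject) = Φ((d - 1.96·s0)/s1) + Φ((-d - 1.96·s0)/s1)

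At 350/350, 13% against 16.86%: s0 and s1 are both about 0.0269, and (0.0386 - 0.0528)/0.0269 = -0.53, so P is about 30%. At 233/467 with a 5.79-point shift, P is about 49%. Simulation (2,000 runs) gave 29.6% and 49.0%. Over 3.0 to 5.4 points a year the ranges are 20-50% and 33-76%.

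**4. Effect of the fewer-than-3-doses criterion.** Women already complete are excluded, so drift acts only through the partly vaccinated share of the remainder:

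- ages 18-26: (30 - 13)/(100 - 13) = 19.5%
- adolescents: (60 - 40)/(100 - 40) = 33.3%
- gradient: (33.3 - 19.5)/7 = 2.0 points per birth year

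Assume partly vaccinated women complete 10 to 50 points more often than unvaccinated women. Drift in the endpoint is then 2.0 × 0.10 = 0.2 to 2.0 × 0.50 = 1.0 points a year. False rejection is about 5-7% at 350/350 and 5-8% at 233/467.

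**5. Direction.** Suppose, for illustration, that 13% of the historical group were already complete at delivery, that these women are kept in, and that everyone else in both periods completes at 13%.

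- Counted as complete, the historical rate is 0.13 + 0.87 × 0.13 = 24.3%, against 13% in the program cohort: 11.3 points against the program.
- Counted in the denominator only, it is 0.87 × 0.13 = 11.3%: 1.7 points in the program's favour.

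The plan does not say how such women are counted.

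**6. What a trend term costs.** For a step at fraction c of a uniform time axis, adding a linear term multiplies the variance of the step by 1/(1 - 3c(1 - c)). This is 4 at c = 1/2 and 3 at c = 1/3, so intervals are 2.0 or 1.7 times wider. False rejection under the 3.86-point drift returns to about 5%. Power for a true 10-point effect falls from 93% to about 41% (350/350) or from 90% to 44% (233/467). The pre-year alone estimates a slope with standard error 100·√(12 × 0.13 × 0.87/n) = 6.2 points a year (n = 350) or 7.6 (n = 233). A drift of 3 to 5 points a year would not be visible in it.

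**The case against.** The strongest reply is that the coverage gradient is the wrong quantity. It comes from two national cross-sectional figures with different sources, and the protocol draws no trend from them. It measures ever having completed, whereas Aim 3 measures completion after delivery in a cohort from which completed women are excluded. This stands under 1.41 and Section I.5, and it takes most of the force out of the 30% and 49% figures. The 49% also needs the two-year reading of the program period, which other sections contradict. It stands less firmly under Section I.7, where no dose limit appears.

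A second reply is that the text only says the proportions will be compared, in a self-described pilot that also measures inpatient acceptance and administration. Section I.2 says the vaccine was not routinely offered to inpatients before, so inpatient receipt is hard to explain by drift. That is fair for uptake. It does not protect the completion contrast. The planned regression could carry a period term, but none is planned.

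A reader might also infer that the other-vaccine data could test for a birth-cohort trend. They cannot. Tdap, influenza and MMR can show a general change in vaccination practice or recording, but not an HPV-specific trend. They were already standard inpatient practice, so they may have little room to move, and that the program leaves them untouched is an assumption. Nor is everything needed clearly on the chart list: delivery date is implied by the follow-up windows but not listed, and the historical-data sentence in 1.43 names only HPV history, although 1.42 suggests that the full list covers both groups.

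**Conclusion.** The point holds as a gap in the analysis that is cheap to narrow. The only contrast with a no-program group is unadjusted, appears in both 1.44 and Section I.12, and supports a stated effectiveness aim.

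Its size is not established. The 3.9 points a year, with false rejection of 30% or 49%, is an upper bound that assumes the whole coverage gradient reaches the endpoint. With the fewer-than-3-doses criterion the drift is nearer 0.2 to 1.0 points a year and false rejection about 5-8%. That rests on the 13% baseline, the mid-age gap and the assumed 10-to-50-point advantage of partly vaccinated women. These figures cover birth-cohort drift only; changes in practice, recording or case mix cannot be sized from the documents. The direction is uncertain while the historical group lacks the dose criterion.

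Two stronger readings are not supported. A reader might infer that the plan attributes the whole difference to the program; it does not say so, although it offers nothing to separate the two. A reader might also infer that the Background shows rising coverage in this population; it makes a rise plausible and does not measure one.

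**What to change.** In 1.44 and Section I.12:

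1. Apply the fewer-than-3-doses criterion to the historical group as well, and align Section I.7.
2. Keep the chi-square, and add a logistic model of completion with a period indicator, age or birth year, and doses received before delivery.
3. As sensitivity analyses, report completion by delivery month, a model with a linear delivery-month term, and the same before/after comparison for Tdap, influenza and MMR. Label the last as a check on general vaccination practice or recording.
4. List delivery date as a chart item, and confirm that other-vaccine data are abstracted for both periods.
5. Report all estimates together and limit causal wording if they disagree. Do not make a claim of effectiveness conditional on the trend model: at about 41-44% power for a 10-point effect, such a rule could veto a real benefit.

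The comparator clinics and the length of the program period should be reconciled in the same edit.

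The cost is revised wording, one explicit data field and a little more analysis. The trend-adjusted interval is about 1.7 to 2.0 times wider, which is why it stays a sensitivity analysis.
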